3.2.2 Study Duration and Study Completion

The study ends approximately 1 year after the last subject in Phase 2 has commenced study treatment. Subjects who complete or discontinue study treatment prior to progression will be followed for clinical and radiological evidence of progression and immunogenicity assessment at least every 3 months until documentation of RECIST v1.1 progressive disease (PD), start of a subsequent anti-cancer treatment regimen, withdrawal of consent, death, or Sponsor notification that follow-up is no longer required, whichever comes first. Best response to first subsequent therapy, AEs which are Grade ≥ 3 , and concomitant medications used to treat these AEs, will also be captured during the follow-up phase of the study (Table 4 and Table 5).

After documentation of PD or use of a subsequent anti-cancer treatment regimen, all subjects will be contacted by telephone every 3 months for a survival follow-up until the site is notified by the Sponsor that survival follow-up is no longer required. A subject has completed the study at the earliest of death or study end.

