⁹ CBC with differential should be done 24 to 48 hours after the IMO-2125 injection, to coincide with the post-injection biopsy (if the biopsy is conducted). Chemistry profile and coagulation tests do not have to be conducted if Screening tests were conducted within 7 days of the Cycle 1 Week 1 Visit.

¹⁰PT, aPTT, INR.

¹¹ Blood pressure, heart rate, respiratory rate, and temperature.

¹² Week 2 ECG pre-dose and at 2 hours post-IMO-2125 administration. Week 11 ECG at 2 hours post-IMO-2125 administration.

¹³ Including assessment of melanoma lesions.

¹⁴ In Phase 2, all tumor biopsies are optional. See Section 13.2 of the protocol and the Laboratory Manual for details on the collection of biopsies and analyses of biomarkers.

¹⁵ Biopsy of the injected tumor should occur within 24 to 48 hours after injection (no more than 48 hours).

¹⁶ In Phase 2, blood biomarker samples will be collected from at least 20 patients treated at the IMO-2125 RP2D after which the Sponsor will determine if additional samples are needed. The blood biomarker samples will be collected on Day 1 before IMO-2125 administration, 4 hours after IMO-2125 administration, and 24 to 48 hours (coinciding with the 24-hour PK sample) after the injection. At Week 2 and Cycle 3 Week 8, collect before ipilimumab or pembrolizumab dosing.

¹⁷ Radiologic assessment and Investigator assessment of response at Week 8, Week 17, and Week 29 may be conducted within a \pm 7-day window.

¹⁸ At least every 3 months until progression, start of next melanoma treatment, withdrawal of consent, death, or Sponsor notification that follow up is no longer required.

¹⁹ In Phase 2, response assessed using irRECIST and RECIST v 1.1. Best response to first subsequent treatment should also be captured. Confirmatory scans for CR, PR, and progressive disease should be performed \geq 4 weeks after the date the response was first documented.

²⁰ To minimize bias in the PRO data, the PRO assessments should be completed before study drug administration and AE assessments.

²¹ For patients assigned to the IMO-2125 + pembrolizumab treatment arm, continued pembrolizumab dosing per the approved product label is permitted at the discretion of the Investigator.

²² PK: blood sampling for analysis of plasma concentrations of IMO-2125 and serum concentrations of ipilimumab, and pembrolizumab (See **Error! Reference source not found.**Table 3 of the protocol for specific collection

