8.1 Best Overall Response

The best overall response is the best response across all disease assessment visits after baseline taking into account requirements for confirmation. For any response criteria, the best overall response for each subject will be determined by examining investigator-assessed visit-level responses and determining the best confirmed response using the assignment rules in Section 8.1.1 or Section 8.1.2, as appropriate (Paules et al, 2010). Only visit-level disease assessments prior to the start of new anti-cancer therapy or response per the appropriate criteria will be considered.

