8.4 Missing Data

Subjects who discontinue from the study before completing an on-study radiographic tumor evaluation will be counted as non-responders in the evaluation of ORR.

Subjects who discontinue from the study or who are lost to follow-up without objective tumor progression while on treatment will be censored on the date of the last assessment documenting absence of disease progression in the evaluation of PFS and DoR. Subjects who discontinue from the study or who are lost to follow-up before death will be censored at the date they were last known to be alive in the evaluation of OS.

The following algorithms will be applied to missing and incomplete start and stop dates (i.e., AEs and concomitant medications):

Start Dates

- If the day portion of the start date is missing, then the start date will be estimated to be equal to the date of first dose of study drug, provided the start month and year are the same as the first dose of study drug and the stop date is either after the first dose of study drug or completely missing. Otherwise, the missing day portion will be estimated as '01'.
- If both the day and month portions of the start date are missing, then the start date will be estimated to be equal to the date of first dose of study drug, provided the start year is the same as the first dose of study drug and the stop date is either after the first dose of study drug or completely missing. Otherwise, the event will be assumed to start on the first day of the given year (e.g., ??-??-2013 is estimated as 01-JAN-2013).
- If the start date is completely missing and the stop date is either after the dose of study drug or completely missing, the start date will be estimated to be the date of first dosing of the study drug. Otherwise, the start date will be estimated to be the first day of the same year as the stop date. All other non-AE and non-concomitant medication day calculations where only partial dates are available will be handled as follows: the first day of the month will be used in the calculations if the day part of a start date is missing and January 1 will be employed if both the month and day parts of a start date are missing.

Stop Dates

- If only the end day is unknown, the day will be assumed to be the last day of the month (e.g., ??-JAN-2013 will be treated as 31-JAN-2013).

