8.5 Efficacy Endpoints

ORR is defined as the proportion subjects with a best confirmed overall response of complete response (CR) or partial response (PR), with assessment of response to be determined by the investigator using irRECIST and RECIST v1.1.

OS is defined as the number of months from initiation of treatment to death from any cause. Subjects who have not died at their last contact will be censored on the date of last contact. The specifications for the time to death calculation are:

- If death is reported either on AE or Death CRF pages, OS will be calculated as *Date of Documentation of (Death – First Dose Date + 1) / 30.4375*.
- Subjects will be censored at their last contact date if death is not reported at the data cut-off date for study closure, and their survival time will be calculated as *(/Last Contact Date - First Dose Date + 1) / 30.4375*). Last contact date is defined as the last date reported among, Adverse Event (AE start date), the Study Exit Status, Hematology, Chemistry, Assessment of RECIST v1.1 Response, Assessment of irRECIST Response, Long Term Follow Up, Study Drug Administration (IMO-2125), ipilimumab Infusion and pembrolizumab Infusion pages of the eCRF.
- Subjects lacking data after the date of first dose who do not die will have their survival time censored on the date of first dose with duration of 1 day.

PFS, defined as number of months from the initiation of treatment to disease progression using RECIST v1.1 or irRECIST or death from any cause, will be calculated as *([Date of Documentation of Death or Disease Progression – First Dose Date + 1]/30.43750*. Subjects without reported progression at their last contact date will be censored on the date of their last valid disease assessment. A valid disease assessment is any disease assessment with overall visit-level response of irCR irPR, irSD, or irPD (without subsequent confirmation) when using irRECIST and CR, PR, or SD when using RECIST v1.1. Subjects who start new anti-cancer therapy before a PFS event will be censored on the date of initiation of new anti-cancer therapy (Subsequent Anti Cancer Therapy eCRF page).

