Duration of response, defined as the length of time from the first occurrence of confirmed response (CR or PR) until confirmed (if necessary) disease progression with assessment of response to be determined by the Investigator using the irRECIST, and RECIST v1.1. DoR will be calculated as *[Date of Documentation of Death or Disease Progression – Date of First Objective Response]/30.4375*. The censoring rules for PFS will be used for DoR. Subjects who

fail to achieve a CR/irCR or PR/irPR during the study will be excluded from the analysis of DoR.

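### PFS and DoR censor subjects who switch therapy on the therapy start date rather than at the last disease assessment, crediting them with unobserved progression-free time

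*SAP*

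**What the plan says.** Section 8.5 gives two PFS censoring sentences that bear on a switcher. The general one is "Subjects without reported progression at their last contact date will be censored on the date of their last valid disease assessment". The specific one, tied to the eCRF page for subsequent therapy, is "Subjects who start new anti-cancer therapy before a PFS event will be censored on the date of initiation of new anti-cancer therapy". The section then states "The censoring rules for PFS will be used for DoR".

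Section 8.4 covers subjects who discontinue the study or are lost to follow-up without objective progression while on treatment. They "will be censored on the date of the last assessment documenting absence of disease progression in the evaluation of PFS and DoR".

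On timing of scans, the footnotes to the Section 3.4 schedules say "Radiologic assessment and Investigator assessment of response at Week 8, Week 17, and Week 29 may be conducted within a" window of seven days either way. After treatment, Section 3.2.2 provides for follow-up "at least every 3 months until documentation of RECIST v1.1 progressive disease (PD), start of a subsequent anti-cancer treatment regimen", among other stopping events. Scanning therefore ends when new therapy starts.

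Section 8.1 limits the data used for response in the same spirit: "Only visit-level disease assessments prior to the start of new anti-cancer therapy" count.

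**The concern.** A therapy start date says nothing about whether the tumour had progressed by then. The last scan does. Moving the censoring date from the scan to the switch leaves the subject in the risk set as progression-free through an interval with no assessment, while other subjects die or are found to have progressed. Because scanning stops at the switch, no later scan can correct the date.

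The affected results are PFS at 6 and 12 months, median PFS, and DoR. The two sentences also overlap with no stated order, so two programmers could derive different PFS datasets from the same text. The SAP gives no reason for the different date and plans no sensitivity analysis.

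**Working it through.** The SAP states no figure for this rule, so there is none to reproduce. The check has four steps.

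**1. Which rule applies.** Take a subject with stable disease at Week 17 who starts new therapy at Week 25 with no further scan. The general sentence gives Week 17 and the specific sentence gives Week 25. Both conditions are met.

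**2. Unobserved time per switcher.** If no scan is missed, this is bounded by the gap between scheduled scans (days divided by 30.4375):

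- first dose (Week 1) to Week 8: 7 weeks = 1.61 months
- Week 8 to Week 17: 9 weeks = 2.07 months
- Week 17 to Week 29: 12 weeks = 2.76 months
- follow-up, 3-monthly (taken as 13 weeks): 2.99 months

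**3. Direction.** The Kaplan-Meier estimate is the product over event times of (1 − d/n). The events are the same under both rules. A later censoring date can only raise n at event times between the last scan and the switch, so each factor rises or stays equal. If no event falls in those intervals, nothing changes.

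**4. Size.** The switching rate, median PFS and share of deaths are not in the SAP and are assumed. The simulation used 200,000 subjects per scenario, exponential event times with median 3 or 6 months, and 20% of events as deaths dated when they occur. Scans fall at Weeks 8, 17 and 29 (±7 days), then every 13 weeks. Of the subjects whose event is not a death, 10, 20 or 30% switch at deterioration, before the next scan. PFS in percent, therapy-start rule against last-scan rule (differences are from unrounded values):

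| Median | Switchers | 6 months | Difference | 12 months | Difference |
|---|---|---|---|---|---|
| 3 mo | 10% | 41.5 v 40.9 | +0.6 | 11.8 v 11.3 | +0.5 |
| 3 mo | 20% | 43.8 v 42.5 | +1.3 | 13.7 v 12.7 | +1.0 |
| 3 mo | 30% | 46.6 v 44.6 | +1.9 | 15.9 v 14.2 | +1.6 |
| 6 mo | 10% | 64.2 v 63.9 | +0.3 | 34.5 v 34.1 | +0.4 |
| 6 mo | 20% | 66.2 v 65.6 | +0.6 | 37.2 v 36.4 | +0.8 |
| 6 mo | 30% | 68.5 v 67.7 | +0.8 | 40.5 v 39.3 | +1.2 |

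The mean credited time is 1.0 to 1.2 months per switcher. A second simulation with scans on schedule gave about 5 to 7 weeks, with +0.2 to +2.1 points at 6 months and +0.4 to +1.6 at 12 months.

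If new therapy starts 13 weeks after deterioration with no scan in between, the credited time is about 4 months. The differences become +0.9 to +6.9 points at 6 months and +1.4 to +6.7 at 12 months.

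If there are no between-scan deaths, no scan-date variation and no missed scans, the two rules give the same curve.

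**DoR illustration.** The smallest rejection boundary is 4 responders of 21 (pembrolizumab arm, Section 4). If one switcher stays at risk through the first event, that step is 3/4 = 75.0% instead of 2/3 = 66.7%, a gap of 8.3 points. With 7 responders (0.35 × 21 = 7.35), it is 6/7 = 85.7% against 5/6 = 83.3%, a gap of 2.4 points.

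**The case against.** The new-therapy sentence follows the general one and names its own eCRF page, so it reads naturally as a deliberate exception. That is fair, and it reduces the overlap to a missing statement of precedence. It does not supply the observations that the later date presumes.

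A reader might infer that the rule contradicts Section 8.4 for every switcher. It does not. Section 8.4 reaches only subjects who discontinue the study or are lost to follow-up. Under Section 3.2.2 a switcher stays in the study under telephone survival follow-up. The clash with Section 8.4 is confined to someone who leaves the study and also starts new therapy.

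A reader might also infer that the rule hides progression in subjects who deteriorate clinically. Appendix C does keep clinical deterioration from being recorded as PD, but it also asks that objective progression be documented even after treatment stops. The reasons for switching are not documented. In any case, if switchers are those about to progress, the censoring is informative under either date. With common scan days, a 3-month median and 20% switchers, 6-month PFS was 49.3% under both rules, against 42.7% when every progression was detected. Changing the date removes none of those 6.6 points.

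The effect is also small beside sampling error. With 21 subjects and PFS near 40%, the binomial standard error is √(0.4 × 0.6 / 21) = 10.7 points, a 95% interval of about ±21. Confirmatory scans at 4 weeks or more shorten some gaps for responders. All of this limits the weight of the point, but a one-directional shift that one sentence can remove is still worth removing.

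**Conclusion.** The point holds as a modest, one-directional bias in secondary endpoints, together with an unstated precedence between two sentences of Section 8.5. Switchers are credited with up to one scan gap of unobserved progression-free time, about 7 to 13 weeks, and more after a missed scan. Under the assumptions above, 6- and 12-month PFS are raised by roughly 0.2 to 2 points with scans on schedule, by several points if scans are missed and switching is common, and not at all if every event falls on a common scan day. The direction follows from the estimator; the size rests wholly on the assumed inputs. A single switcher weighs more in DoR, but only the illustration above was worked out there.

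The documents do not support reading this as a threat to the trial's main conclusion. PFS and DoR are Kaplan-Meier summaries without a hypothesis test, and the alpha-controlled tests are on ORR, which this rule does not touch.

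**What to change.** In Section 8.5, replace the new-therapy sentence with one stating that subjects who start new anti-cancer therapy before a PFS event are censored at the last valid disease assessment on or before that start date. If there is none, they are censored at the first dose date with a duration of 1 day. Section 8.5 gives such a fallback only for OS at present. The rule then carries to DoR through the existing cross-reference.

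One addition is needed for irRECIST. Section 8.5 counts irPD without later confirmation as a valid assessment, and confirmation takes at least 28 days. A subject who switches in that window would still be censored as event-free at the scan that showed growth. State how such a subject is handled, for example with a sensitivity analysis that counts the unconfirmed irPD as an event.

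The report should also acknowledge that censoring of switchers may be informative whichever date is used.

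The cost is one replaced sentence, one added sentence for irRECIST and a small programming change. PFS and DoR may come out slightly less favourable.

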8.6 Interim Analysis

There are 3 interim and 1 final analyses planned:

- A planned analysis of phase 1 results at the completion of dose escalation for both combinations will be conducted.
- An analysis of the safety and efficacy results in each phase 2 arm will be conducted separately after 21 subjects in the primary efficacy population (used in the two-stage design) have had at least 2 post-baseline disease assessments.
- The final analysis by efficacy populations of all subjects in the IMO-2125 + ipilimumab arm will be done when all subjects have had at least 2 post-baseline disease assessments.

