2.2 Secondary Objectives

The secondary objectives of Phase 1 are to determine the plasma pharmacokinetics (PK) of single-dose IMO-2125 and repeat-dose IMO-2125 PK administered intratumorally in combination with ipilimumab and pembrolizumab. An additional secondary objective of Phase 1 is to describe any preliminary antitumor activity.

The secondary objectives of Phase 2 are to further assess the safety and tolerability of IMO-2125 in combination with ipilimumab or in combination with pembrolizumab in subjects with metastatic melanoma and to assess treatment response using RECIST v1.1 and irRECIST, overall survival (OS), OS at 6 months and 12 months, progression-free survival (PFS), PFS at 6 months and 12 months, durable response rate (DRR), duration of response (DoR), and disease control rate (DCR).

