9.3.2 Evaluation of Time to Event Endpoints

The OS and PFS proportions will be estimated at 6 and 12 months; OS and PFS will also be analyzed overall with Kaplan-Meier estimate including median. For time-to-event endpoints (OS, PFS, and DoR), the Kaplan-Meier method will be used to estimate the probability of event-free survival. The analyses of OS, PFS, and DoR will only be done for the subjects treated at the RP2D for each treatment arm.

Kaplan-Meier plots will be produced for OS and PFS by treatment arm. Subgroup analysis of overall survival at 6 and 12 months, as well as progression-free survival, may be performed for the 8 mg IMO-2125 and ipilimumab combination dose group if data supports it.

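### SAP section 8.6 times every Phase 2 analysis it lists, including the only final one, at two post-baseline assessments: too early for the 6- and 12-month and durable-response endpoints promised in both arms

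*SAP*

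**What the plan says.** Section 8.6 opens with a count: "There are 3 interim and 1 final analyses planned". Its bullets account for all four:

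- one analysis of Phase 1;
- one analysis in each of the two Phase 2 arms, "after 21 subjects in the primary efficacy population (used in the two-stage design) have had at least 2 post-baseline disease assessments";
- one final analysis, confined to the ipilimumab arm: "The final analysis by efficacy populations of all subjects in the IMO-2125 + ipilimumab arm will be done when all subjects have had" the required number of scans, the criterion again being that they "have had at least 2 post-baseline disease assessments".

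The secondary objectives in section 2.2 apply to both combinations and include "overall survival (OS), OS at 6 months and 12 months, progression-free survival (PFS), PFS at 6 months and 12 months", together with DRR, duration of response and disease control. Section 9.3.2 adds: "The OS and PFS proportions will be estimated at 6 and 12 months". On scope it says: "The analyses of OS, PFS, and DoR will only be done for the subjects treated at the RP2D for each treatment arm". Section 9.3.1 defines DRR as a response of about 6 months that begins within 12 months of first dose, reported by arm as a percentage with an exact confidence interval.

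Two other sections bear on timing. Section 8.5 censors OS at last contact when no death is reported by the cut-off for study closure. Section 3.2.2 puts study end about one year after the last Phase 2 subject starts treatment.

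**The concern.** The listed analysis times suit a response-rate endpoint, not the time-based secondary endpoints. A cut at the second scan leaves the most recently treated subjects well short of 6 months, let alone 12. Kaplan-Meier estimation copes with that for OS and PFS at the price of precision. DRR has no such protection: a responder whose response has not yet been observed for 6 months counts as not durable, whatever happens later.

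Section 8.5 implies a later cut for OS, but section 8.6 schedules nothing at it. Someone programming from section 8.6 therefore has no instruction to produce OS, PFS, duration of response or DRR at closure for either arm. In an open-label trial with investigator-assessed response, that leaves the choice of data cut open after results have been seen.

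The second problem is the wording of the ipilimumab trigger. It makes no exception for subjects who can never have a second assessment.

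**Working it through.** The SAP gives no figure for analysis timing, so there is none to reproduce. Its two-stage design figures do reproduce (power 77% and 96%, expected sample sizes 13.33 and 14.41) and do not depend on this point.

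**Follow-up at the cut.** Section 3.4 sets the scans: "Radiologic assessment and Investigator assessment of response at Week 8, Week 17, and Week 29 may be conducted within a" 7 days either side. Section 8.5 converts to months as (days from first dose + 1) / 30.4375.

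- Week 17 is Day 7 × 16 + 1 = 113, and 113 / 30.4375 = 3.71 months.
- With the window: 106 / 30.4375 = 3.48 to 120 / 30.4375 = 3.94 months.
- Shortfall for the last subject: 6 − 3.71 = 2.29 months and 12 − 3.71 = 8.29 months.
- If a confirmatory scan 4 weeks after Week 8 counts as the second assessment, the cut could come at Day 78: 78 / 30.4375 = 2.56 months.

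**Landmark maturity.** The SAP gives no accrual period, so uniform accrual over A months is assumed. The share with potential follow-up of at least t months is (A + 3.71 − t) / A, with a floor of 0.

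| A (months) | at least 6 months | at least 12 months |
|---|---|---|
| 6 | 62% | 0% |
| 12 | 81% | 31% |
| 18 | 87% | 54% |
| 24 | 90% | 65% |

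**DRR.** Section 9.3.1 measures length as (end date − first response date + 1) / 30.4375.

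- First response at Week 8 (Day 50), cut at Week 17 (Day 113): (63 + 1) / 30.4375 = 2.10 months.
- Six months by this formula needs 6 × 30.4375 − 1 = 181.6, so 182 days. A Week 8 responder gets there on Day 50 + 182 = 232, and 232 / 30.4375 = 7.62 months after first dose.
- Subjects who start within 7.62 − 3.71 = 3.91 months of the last subject therefore cannot yet count as durable. Under the same assumed accrual, that is 3.91 / A: 65%, 33%, 22% and 16% of the arm for A = 6, 12, 18 and 24.

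**Ipilimumab final-analysis trigger.** Section 3.1.2 allows up to 60 subjects at the ipilimumab RP2D. If each independently has probability q of no second assessment (assumed), the trigger is blocked with probability 1 − (1 − q)^60:

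- q = 2%: 70%
- q = 5%: 95%
- q = 10%: 99.8%

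The SAP itself expects such subjects. Section 8.4 counts those with no on-study scan as non-responders, and section 6 requires no scan for the efficacy populations. Section 3.1.2 replaces only losses before the first evaluation, and not those due to toxicity.

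**Per-arm trigger.** This needs 21 subjects with two assessments, not all subjects. In the pembrolizumab arm, one loss blocks it only if the population is exactly 21.

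**The case against.** A reader might infer that later pembrolizumab data would never be analysed. The SAP does not support that. Section 8.5 names a study-closure cut-off for OS, section 3.2.2 keeps the study open about a year after the last Phase 2 start, and section 9.3.2 promises OS, PFS and duration of response in each arm. Nor is the list in section 8.6 wholly exhaustive: the Stage 1 futility look in section 3.1.2 is not on it. What remains is that section 8.6 links no analysis to closure.

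A reader might also see a defect peculiar to the pembrolizumab arm. The ipilimumab final analysis has the same criterion and the same minimum follow-up, so being listed as final gives it no better maturity. The asymmetry also has a design reason: pembrolizumab enrolment stops at 21 evaluable subjects, whereas ipilimumab continues in two populations.

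Third, it is tempting to say that one early death blocks every trigger. That holds only for the ipilimumab final analysis. The ipilimumab per-arm count can be filled by later subjects, since at least 21 are planned. A replaced pembrolizumab subject who received both drugs stays in the population and can take it above 21.

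Finally, 3.7 months describes the last subject only. Entry is staggered, Phase 1 subjects at the RP2D count, and Kaplan-Meier handles censoring. This is right for OS and PFS, which would usually be immature rather than inestimable. It does not help DRR.

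**Conclusion.** The point stands as a mismatch between the analysis times in section 8.6 and the endpoints in sections 2.2, 9.3.1 and 9.3.2, in both arms. The minimum follow-up of about 3.7 months comes from the SAP's own schedule and conversion. The landmark estimates would be immature to a degree that depends on accrual. With accrual as short as 6 months, no subject could reach 12 months, the longest follow-up being 6 + 3.71 = 9.71 months.

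The downward bias in DRR follows from its definition. Its size depends on accrual, with 16% to 65% of an arm unable to count as durable in the cases assumed.

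Read literally, the ipilimumab final-analysis trigger fails after a single early death, withdrawal or loss, which is likely in up to 60 subjects even at an assumed 2% loss. Section 8.4 suggests loose wording rather than an intention to wait indefinitely, but the text should say so. Only secondary, descriptive endpoints are touched. The primary ORR test and the two-stage operating characteristics are unaffected, so this should be corrected but does not undermine the design.

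**What to change.** In section 8.6:

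1. Add a final analysis of OS, PFS, duration of response and DRR for both arms at the study-closure cut-off that section 8.5 already names, about one year after the last Phase 2 subject starts. Label earlier results for these endpoints as interim.
2. Reword the triggers so that a subject qualifies on having two post-baseline assessments, or progression, death, new anti-cancer therapy, withdrawal or loss to follow-up before then.

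Closure gives each surviving Phase 2 subject still in follow-up about 12 months. DRR allows a response to begin up to month 12 and then needs about 6 more (12 + 6 = 18), so late responders could still be cut short. A sentence on how responders with less than 6 months of observed response are reported would cover them.

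The cost is SAP wording and one data cut at closure.
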